10.10.1 Medically Necessary MRI Scan Source Documentation Requirements

Data and source documentation requirements for medically necessary MRI scans are listed in **Table 10-17**.

Data Collection	Retention of Original Source Documentation	
EMPOWER Programmer Reports:		
- Initial EMPOWER Combined Follow-up Report	Study site	

 
Interim Combined Follow-up Report with MRI settings documented (based on the mCRM and EMPOWER MRI Tech Guide)
 
		
- EMPOWER Real-Time Log Report (to document LOC prior to and after MRI scan)		
- Final EMPOWER Combined Follow-up Report		
S-ICD Programmer Reports:	Study site; upload copy to BSC via study EDC system	

 
S-ICD Summary Report showing MRI Protection
 
Mode programming
 
		
- S-ICD Summary Report After the MRI Scan		
- Full S-ECG Report(s) Treated, if applicable		
- Full S-ECG Report(s) Untreated, if applicable 		
Communication Test S-ECG Reports	Study site	
Reportable Adverse Events, Device Deficiencies, and Protocol Deviations, if applicable	Study site	
Data items that do not have an original source document will be collected on a TSF	Study site	

# Table 10-17: Medically Necessary MRI Scan Visit Data Collection and Source Documentation Requirements

#### 10.11 LATITUDE Monitoring

Subjects may be followed using the LATITUDE™ NXT Patient Management System from the time they are implanted with the S-ICD System. Note that LATITUDE surveillance of the EMPOWER PG will not be available during the study.

Spontaneous episodes can be collected via the LATITUDE NXT System, if applicable, but this does not replace the Semi-Annual in-clinic visits, nor does it replace the requirement to upload all device episodes in the study database. Required MODULAR ATP Clinical Study follow ups cannot be substituted with a LATITUDE remote follow up.

<sup>34 Note that AF diagnostic episodes labelled "Full S-ECG Report AF" are NOT required.

### 10.12 Revisions, Replacements and Explants

If the S-ICD electrode, S-ICD PG, and/or EMPOWER PG are surgically revised, explanted, or removed from service after the initial implant procedure, or the S-ICD PG, EMPOWER PG is permanently programmed off, or disabled, the associated Device Tracking Form is used to record changes to the system, including rationale for the change.

Subjects with the EMPOWER PG or S-ICD with clinical firmware implanted will continue to be followed in the study. Subjects undergoing explant of the mCRM Coordinated System must be followed at least 30 days post-explant (either in-clinic or phone contact) to assure there are no associated adverse events, or to assure the resolution of any adverse events associated with the explant. These subjects must be withdrawn from the study after satisfying the follow-up period of at least 30 days; refer to **Section 9.5** for more information on study withdrawal.

If the EMPOWER PG is retrieved, procedure times of the device retrieval including fluoroscopy time, sheath in/out times, and retrieval catheter in/out times, as well as the outcome of the retrieval procedure will be collected. The explanted EMPOWER PG must be returned to BSC for returned product analysis. A copy of the Combined Follow-up Report from the programmer before the EMPOWER PG is taken out of service or explanted should be obtained. If the S-ICD with clinical firmware is explanted, it must be returned to BSC for returned product analysis. A copy of the S-ICD Summary Report before the S-ICD is taken out of service or explanted should be obtained. Table 10-18 lists the data required for system revisions.

Document any subsequent implant of another EMPOWER PG or S-ICD, regardless whether the previous EMPOWER PG is explanted or not, on the appropriate eCRF. These subjects should continue with the original follow-up schedule established using the initial Time 0.

Regardless of which device is revised or replaced, collect the following data.

#### **10.12.1 EMPOWER PG Evaluation**

PCT, Pacing Impedance, and R-wave Amplitude are required to be measured. Collect PCT measurements according to **Section 10.3.1.7**.

It is required to retain the "Real-Time Log Report" from the EMPOWER PG programmer, documenting at a minimum the LOC portion of the threshold testing (i.e., the lowest voltage setting demonstrating capture and the highest voltage setting that fails to capture). This documentation will be retained at the study site.

If more than one set of electrical measurements are recorded, the final set must be used for the study.

#### **10.12.2 S-ICD Evaluation**

It is required to retain the "S-ICD Summary Report" from the programmer, documenting initial and final parameter settings, episode counters, etc.

#### 10.12.3 mCRM Coordinated System Programming

Recommended programming parameters for the EMPOWER PG and S-ICD are included in **Sections 10.4.4.1** and **10.4.4.2**, respectively.

Print out a copy of the final "Combined Follow-up Report" and a copy of the "S-ICD Summary Report". Once all study activities are completed at the end of the visit, reset the EMPOWER PG brady counters/ histograms and tachy counters.

#### 10.12.4 Revisions, Replacements, and Explants Data and Source Documentation Requirements

Data and source documentation requirements for revisions, replacements, and explants are listed in **Table 10-18**.

# Table 10-18: Revisions, Replacements, and Explants Data and Source Documentation Requirements

Data Collection	Retention of Original Source Documentation	
- Newly implanted product and accessories utilized for S-ICD System (model/serial/lot/batch/etc.), if applicable		

 
Newly implanted product and accessories utilized for the EMPOWER MPS (model/serial/lot/batch/etc.), if applicable
 
	Study site	
S-ICD Programmer Printouts: - S-ICD Summary Report - Full S-ECG Report(s) Treated, if applicable Full S-ECG Report(c) Untroated if applicable 	Study site; upload copy to BSC via study EDC System	

 
- Chest x-ray (P/A and Lateral), to document mCRM
 
Coordinated System placement
 
- Fluoro or cine images of EMPOWER PG final position
 
	Study site	
Reportable Adverse Events, Device Deficiencies, and Protocol Deviations, if applicable	Study site	
Data items that do not have an original source document will be collected on a TSF	Study site	

#### 10.13 Study Completion

All subjects enrolled in the MODULAR ATP Clinical Study will be followed per the defined follow-up schedule until they withdraw from the study or until BSC notifies study sites of follow-up completion for the study. Subjects will receive standard of care by their

<sup>35 Note that AF diagnostic episodes labelled "Full S-ECG Report AF" are NOT required.

physician after their study participation is completed. Refer to **Section 9.8** for more information.

#### 10.14 Source Documents

It is preferable that original source documents are maintained, when available. In lieu of original source documents, certified copies are required to be maintained. A certified copy is a copy (irrespective of the type of media used) of the original record that has been verified (i.e., by a dated signature or by generation through a validated process) to have the same information, including data that describe the context, content, and structure, as the original.

# **11** Statistical Considerations

# 11.1 MODULAR ATP Clinical Study Endpoints

Each MODULAR ATP Clinical Study endpoint will describe which subjects are eligible for inclusion in the analysis of that endpoint.

#### 11.1.1 Safety Endpoint 1: Major EMPOWER MPS System- and Procedure-related Complication-Free Rate from Implant through 6 Months Post-Implant

Safety Endpoint 1 will be assessed for subjects who undergo any portion of the EMPOWER PG implant procedure. Safety will be confirmed by evaluating the Major EMPOWER MPS-related Complication-free rate (CFR) between the EMPOWER PG implant procedure date and 180 days (6 months) post-implant procedure date. For the purpose of this endpoint, a major EMPOWER MPS-related complication will be defined as those complications that are related to the EMPOWER MPS (pacemaker and/or delivery catheter), or its implant procedure and that are identified as major complications. Major complications are defined as those adverse events resulting in:

- Death
- Permanent loss of device (EMPOWER PG) function due to mechanical or electrical dysfunction of the device (e.g., pacing function disabled, leaving device abandoned electrically)
- Hospitalization
- Prolonged Hospitalization by at least 48 hours
- System revision (reposition, replacement, explant).

At a minimum all complications that the study site reports as EMPOWER MPS-related will be adjudicated by an external committee to identify events that will meet the endpoint definition. Major complications that are determined to be related to the EMPOWER PG or its implant procedure by the external committee will be considered

<sup>36 Planned hospitalization for a pre-existing condition, or a procedure required by the clinical investigational plan, without serious deterioration in health, is not considered a serious adverse event or Major complication.

<sup>37 Hospitalization is extended by  $\geq$ 48 hours beyond expected hospital discharge (from implant or hospital admission for another cause)

major EMPOWER MPS-related complications and will count against this endpoint. For the purpose of this endpoint, the adjudication of the CEC will be used.

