#### 11.5.2 Control of Systematic Error/Bias

Selection of patients will be made from the Investigator's usual patient population. All patients meeting the eligibility criteria and having signed the ICF will be eligible for enrollment in the study. To control for inter-observer variability among sites, an independent CEC will determine the EMPOWER MPS System- and Procedure-related complications to be used in the analysis of Safety Endpoint 1.Number of Subjects per Study Site

To avoid any study site effect and bias, no study site will be authorized to implant or attempt more than 20% of the maximum number of subjects without approval from BSC. A minimum of 50% of total enrollments from North America will be maintained.

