## 21.2 Clinical Events Committee

A Clinical Events Committee (CEC) is an independent group of individuals with pertinent expertise that reviews and adjudicates all treated spontaneous episodes with available source documentation, relevant AEs, and all subject deaths reported by study investigators. Relevant AEs are those deemed to be attributed to either/ both of the PGs in the mCRM Coordinated System, the S-ICD electrode, or the procedure to implant the EMPOWER PG. The CEC will review a safety event dossier for each submitted AE or death, which may include copies of subject source documents provided by study sites, BSC reserves the right to submit other AEs as well, if deemed necessary.

Committee membership will include practitioners of cardiology, as well as other experts with the necessary therapeutic and subject matter expertise to adjudicate the event categories outlined above. CEC responsibilities, qualifications, membership, and committee procedures are outlined in the CEC charter.

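### Non-fatal events that a site attributes to no system component and not to the EMPOWER procedure have no mandatory route to the CEC

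*Protocol*

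**What the plan says.** Four parts of the Protocol decide which events the CEC sees.

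- **Section 11.1.1 (Safety Endpoint 1).** The referral floor is "At a minimum all complications that the study site reports as EMPOWER MPS-related will be adjudicated by an external committee". The committee's decision then governs: "For the purpose of this endpoint, the adjudication of the CEC will be used". Section 11.1.2 uses the same event definition for Safety Endpoint 2.
- **Section 21.2 (Clinical Events Committee).** The scope here is wider. The CEC adjudicates treated spontaneous episodes that have source documents, plus "relevant AEs, and all subject deaths reported by study investigators". It then defines the middle group: "Relevant AEs are those deemed to be attributed to either/ both of the PGs in the mCRM Coordinated System, the S-ICD electrode", or the EMPOWER implant procedure. It does not say who makes that attribution. Anything else is at the sponsor's option: "BSC reserves the right to submit other AEs as well, if deemed necessary".
- **Section 19.5 (Investigator Reporting Requirements).** The investigator assesses the relationship of each reportable event to device, therapy or procedure.
- **Section 11.5.2 (Control of Systematic Error/Bias).** To deal with differences between observers at different sites, "an independent CEC will determine the EMPOWER MPS System- and Procedure-related complications to be used in the analysis of Safety Endpoint 1". Safety Endpoint 2 is not named there.

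Under 19.2 every serious adverse event is reported to the sponsor whatever its attribution. Under 21.1 the DMC oversees all adverse events.

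**The concern.** Section 11.5.2 relies on the CEC to even out how sites judge relatedness. For one class of event that judgement is made before the CEC is involved and decides whether the CEC is involved at all. Take a hospitalization for pericardial effusion, access-site bleeding, infection or worsening heart failure that a site puts down to underlying disease. If the site attributes it to neither pulse generator, the electrode nor the EMPOWER procedure, nothing in the plan requires adjudication. An event that the site does call EMPOWER-related is always adjudicated and can be ruled out of the endpoint.

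The study is single-arm, the investigator knows the treatment, and both safety endpoints are tested against a fixed performance goal. There is no control arm in which the same under-attribution would occur and cancel. Every true endpoint event that never reaches the CEC raises the complication-free rate directly.

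**Working it through.** **1. Routes to the CEC, side by side**

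| Event (non-fatal unless stated) | Must the CEC see it? | Source |
|---|---|---|
| Site calls it EMPOWER-related, major or not | Yes | 11.1.1, 21.2 |
| Attributed to the S-ICD pulse generator or electrode | Yes | 21.2 |
| Death, any attribution | Yes | 21.2 |
| Attributed to no component and not to the EMPOWER procedure | No; sponsor's discretion, no trigger stated | 21.2 |

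The second and third rows, and events in the first row that the site did not regard as major, are ways in which the CEC can add to the endpoint count. The last row is the gap. Reporting all SAEs to the sponsor (19.2), sponsor review of reported events (19.6) and DMC oversight (21.1) do not send last-row events to the CEC.

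**2. The plan's own figures for Safety Endpoint 1**

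Inputs (synopsis table and 11.1.1.2): goal p0 = 0.86, expected p1 = 0.93, one-sided alpha 0.025, power 90%, information fraction 0.6, power-family spending with rho = 1.5, attrition 25%.

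- Interim alpha: 0.025 × 0.6^1.5 = 0.0116, stated as 1.2%.
- Final nominal alpha, from the bivariate normal with correlation √0.6: 0.0188, stated as 1.9%.
- A two-look z-test with null variance needs 223 subjects (interim 134), with power 90.1%.
- 223/0.75 gives 298 and 134/0.75 gives 179.

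All of these match the plan.

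**3. How many events pass**

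With no censoring, e events in n subjects give S = 1 − e/n and SE = √(e/[n(n−e)]). The log-log lower limit is exp(−exp(ln(−ln S) + z·SE/|ln S|)), with z = 2.257 for 1.2% and 2.075 for 1.9%.

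| Look | Events | Lower limit | Against 86% |
|---|---|---|---|
| Interim, n = 134 | 9 | 86.3% | pass |
| Interim, n = 134 | 10 | 85.4% | fail |
| Final, n = 223 | 20 | 86.1% | pass |
| Final, n = 223 | 21 | 85.6% | fail |

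At the planned 93% the expected counts are 134 × 0.07 = 9.4 and 223 × 0.07 = 15.6. The interim threshold therefore lies at about the expected count, and one unreferred event can change the interim result.

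**4. Effect of non-referral (illustration)**

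Let m be the share of all true endpoint events that never reach the CEC. The documents give no value; 0% to 20% is assumed. The counted event probability is q = (1 − true rate)(1 − m). The pass probability is P(X₁₃₄ ≤ 9) + Σ P(X₁₃₄ = e)·P(X₈₉ ≤ 20 − e), summed over e = 10 to 20, with binomial counts and 89 = 223 − 134.

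| m | q at true 86% | False pass at 86% | Pass at true 93% |
|---|---|---|---|
| 0% | 0.140 | 1.9% | 90.1% |
| 5% | 0.133 | 3.6% | 93.4% |
| 10% | 0.126 | 6.5% | 95.8% |
| 20% | 0.112 | 18.4% | 98.6% |

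**5. Safety Endpoint 2**

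For goal 81%, alpha 2.5% and no censoring, the same limit passes with at most 12 events in 112 (CE Mark cohort) or 28 in 210 (the plan's expected Post-Market 1 number). At a true rate of 81%, q = 0.19(1 − m). For m = 0%, 5%, 10% and 20% the false-pass probability is 1.3%, 2.4%, 4.2% and 11.4% with 112 subjects, and 1.9%, 4.2%, 8.4% and 26.0% with 210.

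**The case against.** A reader might infer that only complications which sites call EMPOWER-related must be adjudicated, so that apart from deaths the CEC can do little but remove events. The documents do not support that. Section 21.2 also refers events attributed to the S-ICD pulse generator or electrode, and the CEC could reassign those to EMPOWER. Section 11.1.1 refers every complication that a site calls EMPOWER-related, not just major ones, so the CEC can raise an event to major. Deaths are referred whatever their attribution. These are real upward routes, and this part of the objection stands.

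It is also fair that the wording in 11.1.1 is a floor, that 21.2 leaves open who makes the attribution, and that the sponsor may send further events. The CEC charter and the relatedness criteria in Table 26-4 are not in the copy available here, and either could make referral broader. Section 10.12 requires revisions, explants and permanent programming-off to be recorded with a rationale, and explanted EMPOWER devices to be returned for analysis. Monitors have access to source documents. These safeguards make a large missed share less plausible for revisions and loss of function than for hospitalizations. None of them obliges anyone to send an unattributed event to the CEC.

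Finally, the non-referral shares are assumed. The calculation ignores sponsor referral, upward reclassification and censoring, and its false-pass figures apply only at exactly 86% or 81%. At the planned 93%, the extra passes are correct ones. That limits the figures to direction and scale; it does not remove the gap.

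**Conclusion.** The concern holds for a defined class: non-fatal events that the site attributes to neither pulse generator, the S-ICD electrode nor the EMPOWER implant procedure. For these, the Protocol requires no adjudication and states no rule for the sponsor's discretion. The CEC can correct many site judgements, but not this one, and it is part of the variability between sites that 11.5.2 says the CEC controls. The bias runs towards passing Safety Endpoints 1 and 2.

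The size cannot be read from the documents. Under the stated assumptions, non-referral of 5% of true endpoint events takes the false-pass probability for Safety Endpoint 1 from 1.9% to 3.6%, which exceeds the 2.5% that 11.5.1 sets as the limit; 10% takes it to 6.5%. This does not show that such under-referral will occur, or that the CEC as a whole works in one direction. The text leaves an avoidable gap, and closing it is a cheap improvement.

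**What to change.** In 11.1.1 and 21.2, state that for both safety endpoints the CEC receives, regardless of site attribution and within 365 days of the EMPOWER procedure:

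- every reported event that led to revision, replacement, explant or loss of function of the EMPOWER PG; and
- every cardiac, vascular, infectious or device- or access-site SAE that led to hospitalization or prolonged hospitalization.

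Deaths are already referred and need no change. Amend 11.5.2 to name Safety Endpoint 2 alongside Safety Endpoint 1. If the CEC charter already contains such a rule, carry it into the Protocol, since these sections determine what counts as an endpoint event.

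The cost is more source-document requests to sites, because Table 19-1 makes SAE documents available at the sponsor's request, and more dossiers for the existing committee. In this population cardiac hospitalizations may make up much of that load. Sample size, alpha and visits do not change, and SAEs are already reported whatever their attribution.

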#### 11.1.1.1 Hypotheses

The following hypotheses will be used to evaluate Safety Endpoint 1 from implant through 6 months post implant:

H0: The Major EMPOWER MPS System- and Procedure-related complication-free rate through 6 months is  $\leq 86\%$ 

 $H_A$ : The Major EMPOWER MPS System- and Procedure -related complication-free rate through 6 months is > 86%.

#### 11.1.1.2 Sample Size

A group sequential design based on the z test of a binomial proportion will be used to assess the Safety Endpoint 1. The assumptions and parameters pertaining to this endpoint are as follows:

- Performance Goal: 86% Major EMPOWER MPS System- and Procedure-related CFR through 6 months post-implant
- Attrition: 25% of enrolled subjects through the 6-month visit
- Power = 90%
- Alpha < 2.5% (1-sided)
- Alpha boundary determination: A power error spending function will be used with  $\rho=1.5$

#### • Number of analyses: 2

• Timing of analyses: The single interim endpoint analysis will occur after a minimum of 134 subjects who have undergone any portion of the EMPOWER PG implant procedure have been followed for 6-months (based on a required 0.6 Information Fraction for the interim analysis). The final analysis of this endpoint may occur when 223 subjects who have undergone any portion of the EMPOWER PG implant procedure have been followed for 6-months if the null hypothesis of Safety Endpoint 1 is not rejected at the interim analysis.

Based on these assumptions and parameters, a sample size of 134 subjects is required for the interim analysis with an alpha of 1.2%. If the null hypothesis is not rejected at the interim analysis, a sample size of 223 subjects is required for the final analysis with an alpha of 1.9%.

### 11.1.1.3 Statistical Methods

Endpoint analysis will be performed on data from subjects that have undergone any portion of the EMPOWER PG implant procedure, including subjects that do not have the EMPOWER PG successfully implanted. The major EMPOWER MPS System and Procedure-related CFR from the date of the EMPOWER PG implant procedure through 6 months (180 days) post-implant will be calculated using Kaplan-Meier methodology.

The interim analysis will be conducted once 134 subjects have undergone the EMPOWER PG implant procedure and have been followed for 6 months (180 days). Using the allocated alpha level of 1.2% for the interim analysis, the 98.8% one-sided lower pointwise confidence limit of the Major CFR will be calculated via log-log methodology and compared to the performance goal of 86%. If the lower confidence limit exceeds 86%, the null hypothesis will be rejected.

If the interim analysis does not result in the rejection of the null hypothesis, the final analysis will be conducted once 223 subjects have undergone the EMPOWER PG implant procedure and have been followed for 6 months (180 days). Using the allocated alpha level of 1.9% for the final analysis, the 98.1% one-sided lower pointwise confidence limit of the Major CFR will be calculated via log-log methodology and compared to the performance goal of 86%. If the lower confidence limit exceeds 86%, the null hypothesis will be rejected.

The Kaplan-Meier methodology was chosen for this endpoint to utilize all available data for each subject. To assess the robustness of this analysis method and the potential impact missing data could have had on the analysis results, a tipping point analysis will be conducted that will include subjects that have undergone any portion of the EMPOWER PG implant procedure, including subjects that do not have the EMPOWER PG successfully implanted. The tipping point analysis will assign each subject with missing data as either having or not having a Major EMPOWER MPS System- and Procedurerelated complication. All possible combinations of these subjects' data will be evaluated along with the actual observed data to find the point, if any, at which the endpoint is failed.

